8.3. Premature Subject Withdrawal

All subjects will be advised that they are free to withdraw from participation in this study at any time, for any reason, and without prejudice. The investigator should make every reasonable attempt to keep subjects in the study; however, subjects must be withdrawn from the study if they withdraw consent to participate. Investigators must attempt to contact subjects who fail to attend scheduled visits by telephone or other means to exclude the possibility of an AE being the cause of withdrawal. Should this be the cause, the AE must be documented, reported, and followed as described in Section 11.2.

The sponsor reserves the right to request the withdrawal of a subject due to protocol deviations or other reasons.

The investigator also has the right to withdraw subjects from the study at any time for lack of therapeutic effect that is intolerable or otherwise unacceptable to the subject, for intolerable or unacceptable AEs, intercurrent illness, noncompliance with study procedures, administrative reasons, or in the investigator's opinion, to protect the subject's best interest.

If a subject is withdrawn before completing the study, the reason for withdrawal and the date of discontinuation will be recorded on the appropriate page of the electronic case report form (eCRF). Whenever possible and reasonable, the evaluations that were to be conducted at the completion of the study should be performed at the time of premature discontinuation.

8.4. Subject Discontinuation of Study Intervention and Stopping Rules

Subjects who discontinue the study treatment will be asked to return to the study site to undergo ET procedures (see Section 10.2.4.6). If a clinically significant finding is identified (including, but not limited to changes from Baseline) after enrollment, the investigator or qualified designee will determine if any change in participant management is needed. Any new clinically relevant finding will be reported as an AE.

An investigator must discontinue a participant's study treatment for any of the following reasons:

- Pregnancy
- Significant study intervention noncompliance
- If any clinical AE, laboratory abnormality, or other medical condition or situation occurs such that continued participation in the study would result in a significant burden to the participant
- If the participant meets an exclusion criterion (either newly developed or not previously recognized) that precludes further study participation

The reason for discontinuation of study treatment will be recorded on the eCRF. Subjects who sign the informed consent form and are randomized but do not receive the study intervention may be replaced. Subjects who sign the informed consent form, are randomized, and receive the study intervention, and subsequently discontinue study treatment, or are withdrawn from the study will not be replaced.

A participant will be considered lost to follow-up if he or she fails to return for 3 scheduled visits and is unable to be contacted by the study site staff.

The following actions must be taken if a participant fails to return to the clinic for a required study visit:

- The site will attempt to contact the participant and reschedule the missed visit and counsel the participant on the importance of maintaining the assigned visit schedule and ascertain if the participant wishes to and/or should continue in the study.

- Before a participant is deemed lost to follow-up, the investigator or designee will make every effort to regain contact with the participant (where possible, 3 telephone calls and, if necessary, a certified letter to the participant's last known mailing address or local equivalent methods). These contact attempts should be documented in the participant's medical record or study file.
- Should the participant continue to be unreachable, he or she will be considered to have withdrawn from the study with a primary reason of lost to follow-up.

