Assessment; IWRS = interactive web response system; OLE = open-label extension; PK = pharmacokinetic; WOCBP = women of childbearing potential; VIIS = Visual Index for Ichthyosis Severity

- a. Upon signing informed consent and entering the Screening Period, subjects will stop using physical and medical treatments for LI, including balneotherapy, and begin to washout prohibited topical and systemic treatments with designated washout periods, as applicable. Before asking a subject to enter washout, investigators should confirm the subject meets study eligibility criteria, except for LI severity (Inclusion Criterion #3). Washout may be up to 90 days. After completing any necessary Washout Period, subjects must return to the site within 35 days before the Baseline Visit within the 97-day Screening Period to have their LI severity assessed and study eligibility requirements determined. During washout, subjects may continue their standard of care of visible skin (face and scalp) for cosmetic reasons and of extremities (palms/soles) to avoid functional consequences on walking or moving their fingers. In the US/EU, this may include compounded emollients with keratolytics (alpha or beta hydroxyl acids) and/or urea. The investigator should approve and document these standard of care treatments in the electronic case report form (eCRF). If the standard of care treatments of the face and/or palms/soles contain prohibited medications, they must be stopped at the Baseline Visit. Subjects may shower, but not bathe or swim during the Screening Period.
- b. Day 90 procedures should be conducted for subjects who terminate the study early. If a subject discontinues IP, but continues to attend clinic visits, Day 90 will occur as scheduled. Day 90 will be the first visit of the OLE for subjects who choose to continue. Subjects who decide to continue into the OLE will have the following additional procedures: 1) sign informed consent; 2) will be weighed; 3) will be instructed on study drug application; 4) will be given new diaries, and 5) will be provided with study drug.
- c. A Follow-up telephone call will be made within 14 days after Day 90 to subjects who choose not to continue into the OLE to assess any ongoing adverse events.

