10.2.2.7 Visit 6 (Day 90 ±7 days) or Early Termination

The following procedures will be performed on Day 90 in the study clinic:

1. Record responses to DLQI and EQ-5D Quality of Life Questionnaires.
2. Perform a limited physical examination.
3. Record vital signs (blood pressure and pulse).
4. Record concomitant medications and concomitant therapies.
5. Record IGA.
6. Record VIIS.
7. Record roughness assessment.
8. Record palm/sole assessment.
9. Record palm/sole assessment of fissuring.
10. Record ectropion score.
11. At sites where the optional photographic substudy is conducted, take photographs of subjects who have provided informed consent for the substudy.
12. Assess local tolerance.
13. Record AEs and review diary.
14. Perform a 12-lead ECG.
15. Perform a urine pregnancy test for WOCBP.
16. Collect blood and urine for routine laboratory tests (subject must be fasting at least 8 hours) and coagulation panel.
17. Collect a PK blood sample (all subjects).
18. Collect returned study drug tubes; confirm study drug compliance by weighing returned kits (tubes and boxes, but not leaflets) and reviewing diaries.

For subjects who successfully complete (i.e., have reliable visit attendance and compliance with IP application, in the investigator's opinion) the initial 90 days of double-blind treatment and choose to continue into the OLE, this visit will be the first visit of that portion of the study. All efficacy assessments, safety/tolerability assessments, including clinical laboratory testing, PK from Day 90 will be carried over to the OLE and will not be repeated. If the subject chooses to continue into OLE, the following additional procedures will be done:

1. Have the subject sign OLE-specific informed consent.
2. Measure subject's weight.

3. Instruct subject on study drug application, and advise subjects regarding permitted emollient(s) and/or sunscreen for use on nontreatment days; use of emollient(s) on study drug treatment days within 4 hours before or after study drug application is prohibited. Remind subjects that at least 24 hours must have elapsed since IP application before the PK draws at the Day 120 and Day 180 Visits, and not to apply IP on visit days until after the visits.
4. Weigh new study drug kits (tubes and boxes, but not leaflets) and dispense enough additional study drug until next visit (only for subjects who choose to continue into the OLE).
5. Dispense study diary.

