10.2.4.6 Visit 10 (Day 180 ±7 days) or Early Termination

The following procedures will be performed at this study clinic visit:

1. Perform a physical examination.
2. Record vital signs (blood pressure and pulse).
3. Record concomitant medications and concomitant therapies.
4. Record IGA.
5. Record VIIS.
6. Assess roughness.

7. Record palm/sole assessment.
8. Record palm/sole assessment of fissuring.
9. Record ectropion score.
10. Assess local tolerance
11. Record AEs and review diary.
12. Perform a 12-lead ECG.
13. Perform a urine pregnancy test for WOCBP.
14. Collect blood and urine for routine laboratory tests (subject must be fasting at least 8 hours) and coagulation panel.
15. Collect a PK blood sample (all subjects)
16. Collect returned study drug tubes; confirm study drug compliance by weighing returned kits (tubes and boxes, but not leaflets) and reviewing diaries.

10.2.4.7 Follow-up Evaluation – Open-Label Extension (Day 194 or 14 days after End of Open label Treatment/Visit 11)

At 14 days after the last administration of the IP, the following procedures will be performed:

1. Perform a limited physical examination.
2. Record vital signs (blood pressure and pulse).
3. Record any concomitant medications/therapies.
4. Record IGA.
5. Record VIIS.
6. Assess roughness.
7. Record palm/sole assessment.
8. Record palm/sole assessment of fissuring.
9. Record ectropion score.
10. Assess and record AEs occurring since the last evaluation and review diary.
11. Perform a urine pregnancy test for WOCBP.

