10.3.4.2.2 Twelve-lead Electrocardiogram

A standard 12-lead ECG will be performed after the subject has been supine for at least 5 minutes. All ECG recordings will be identified with the subject number, date, and time of the recording. Gel ECG electrodes may be used for ECGs because they are more conductive and cause less trauma on compromised skin. Efficacy assessments should be conducted before ECGs to avoid possible artefact/changes from the ECG.

For subjects in the PK substudy, additional ECGs will be performed postdose during serial blood sampling on Day 1 and Day 30.

If there is a marked prolongation of the QT/QTc interval during treatment, a subject should be discontinued from the IP but remain in the study until full resolution of the event. The DSMB will be informed immediately of such an occurrence.

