11.2.4 Treatment of Adverse Events

Adverse events that occur during the study will be treated, if necessary, by established standards of care. If such treatment constitutes a deviation from the protocol, the subject may be withdrawn for treatment but continue to be followed for efficacy and safety in the study. The decision about whether the subject may continue in the study will be made by the sponsor after consultation with the investigator and/or medical monitor.

If AEs occur in a subject that are not tolerable, the investigator must decide whether to stop the subject’s involvement in the study and/or treat the subject. Special procedures may be recommended for the specific IP, such as the collection of a serum sample for determining blood concentrations of IP, specific tapering procedures, or treatment regimens, as appropriate.

It is not necessary to unblind a subject’s treatment assignment in most circumstances, even if an SAE has occurred. If unblinding is necessary, see Section 9.6 for a description of the unblinding procedures.

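### Section 8.4 sends subjects who stop study drug to the open-label ET list and leaves open whether their scheduled Day 90 visit still takes place

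*Protocol*

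**What the plan says.** Section 8.4 sets one rule for anyone who stops study drug: "Subjects who discontinue the study treatment will be asked to return to the study site to undergo ET procedures (see Section 10.2.4.6". It makes no distinction between the Double-blind Period and the OLE and does not mention later visits. The adult-and-adolescent protocol text in the same file has the same rule and the same link.

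The section cited is headed "10.2.4.6 Visit 10 (Day 180 ±7 days) or Early Termination" and belongs to the open-label extension. The double-blind counterpart is headed "10.2.2.7 Visit 6 (Day 90 ±7 days) or Early Termination", and its first item is "Record responses to DLQI and EQ-5D Quality of Life Questionnaires".

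Other places describe subjects who are off drug but still in the study:

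- Section 2.2, Table 2-1 footnote b: "If a subject discontinues IP, but continues to attend clinic visits, Day 90 will occur as scheduled". The same footnote says "Day 90 procedures should be conducted for subjects who terminate the study early".
- Section 11.2.4, where treatment of an adverse event departs from the protocol: "the subject may be withdrawn for treatment but continue to be followed for efficacy and safety in the study".
- Section 10.3.4.2.2, on marked QT prolongation: "a subject should be discontinued from the IP but remain in the study until full resolution of the event".

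Section 13.1.1 makes the ITT population (all randomized subjects) primary for efficacy. Section 13.1.4.1 places the primary IGA endpoint at Day 90/EOT. It lists DLQI through Day 90 as a secondary endpoint and EQ-5D-5L as exploratory.

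**The concern.** Section 8.4 is where a site looks when a subject stops drug, and it has two defects.

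First, it is silent on what follows the ET visit. A site may take that visit as the last one, while a site reading footnote b keeps the subject on schedule to Day 90. Both can claim to follow the protocol, yet they collect different data from the same kind of subject.

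Second, its only cross-reference leads a double-blind discontinuer to a list written for a later period, in which the quality-of-life questionnaires are not collected.

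At stake is the completeness of Day 90 data in an analysis that counts everyone randomized. Stopping may also differ between arms: Section 5.2 reports that irritation forced less frequent application in the healthy-volunteer study, and Section 11.3.1 makes application-site events AEs of special interest. An SAP can say how to handle a missing visit, but it cannot recover one that was never made.

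**Working it through.** **1. The two ET lists**

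| Item | 10.2.2.7 (double-blind Day 90/ET) | 10.2.4.6 (open-label Day 180/ET) |
|---|---|---|
| Numbered core items | 18 | 16 |
| DLQI and EQ-5D | yes (item 1) | no |
| Photographs (optional substudy) | yes (item 11) | no |
| IGA | yes (item 5) | yes (item 4) |
| VIIS, roughness, palm/sole, fissuring, ectropion | yes | yes |
| Tolerability, AEs, ECG, laboratory tests, PK, drug return | yes | yes |

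The gap of 18 − 16 = 2 items is exactly the questionnaires and the photographs. The wrong link therefore loses no investigator score. It loses DLQI (secondary), EQ-5D (exploratory) and an optional quality check.

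**2. The follow-up rules applied to one case**

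Take a double-blind subject who stops drug on Day 20, for whatever reason, and is willing to keep attending.

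- *Section 8.4 read alone:* one ET visit near Day 20, with IGA but no DLQI. Nothing further is stated.
- *Table 2-1 footnote b:* the subject keeps attending and Day 90 takes place as scheduled. The visits still ahead in Table 2-1 are Days 30, 60 and 90, each with IGA and DLQI.
- *Section 11.2.4:* efficacy follow-up may continue, with the sponsor deciding after consultation.
- *Section 10.3.4.2.2:* the subject stays, but only until the QT event resolves.

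Under both of the first two readings the Baseline and Day 14 values of IGA and DLQI exist. The readings differ in the Day 30, 60 and 90 values and in DLQI at ET.

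**3. How many subjects**

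Inputs from Section 13.2: 120 subjects, 1:1:1, 20% drop-out/nonevaluable, 32 evaluable per arm.

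- Randomized per arm: 120 / 3 = 40.
- Evaluable per arm: 40 × (1 − 0.20) = 32, which reproduces the plan's figure.
- Allowance per arm: 40 − 32 = 8; over three arms, 8 × 3 = 24.

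The protocol does not say how many of these 8 would stop drug yet still be willing to attend Day 90. Without that share, the number affected is taken as 0 to 8 per arm (0 to 24 in all). The upper end would need the whole allowance to be such subjects.

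**The case against.** The strongest reply is that the rest of the protocol already does the right thing. The last double-blind column of Table 2-1 is marked as the ET visit and includes DLQI and EQ-5D. Footnote b assigns Day 90 procedures to early terminators. Section 10 refers sites to the Schedule of Events for the timing of procedures. Section 8.3 asks investigators to try to keep subjects in the study and to do the end-of-study evaluations at premature discontinuation. Section 8.4 itself distinguishes discontinuing treatment from being withdrawn, and it only asks subjects to return; it cancels no visit. The texts can be read together as ET assessments at stopping plus Day 90 if the subject still attends.

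That is fair, and it limits the point to an ambiguity and a wrong link. A joint reading being possible does not make it the one each site adopts.

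A reader might infer three stronger things, none of which the documents support:

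- *That the primary outcome of discontinuers is never observed.* Even the wrongly cited list records IGA, and the endpoint is worded Day 90/EOT. What may be lost is the on-schedule value. How an early EOT score counts may be left to the SAP, which is not shown.
- *That a secondary endpoint is lost.* Only DLQI at ET and later is at risk, and only where a site follows 8.4 against Table 2-1. Earlier values remain for the repeated-measures model.
- *That the effect estimate becomes almost unbounded.* With 70% v 40% among 32 observed and 8 unobserved per arm, active ranges over 22.4/40 = 56% to 30.4/40 = 76% and vehicle over 12.8/40 = 32% to 20.8/40 = 52%, a difference of 4 to 44 points. That is the generic bound for 20% missing data. It assumes no IGA at all for the 8 and attributes the whole allowance to 8.4, although the allowance is not broken down by cause.

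The supporting passages are also unequal. Only footnote b mentions Day 90, and conditionally; 11.2.4 is permissive; the QT rule is time-limited. Under Section 9.4, local reactions lead first to less frequent application or a pause on the affected area, so irritation does not automatically mean discontinuation.

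**Conclusion.** The point holds as an inconsistency worth correcting. Section 8.4 cites the wrong ET list for the Double-blind Period and does not say whether scheduled visits continue, whereas footnote b and, permissively, 11.2.4 provide for follow-up off drug. A site following 8.4 alone could miss the on-schedule Day 90 assessments, and DLQI at ET and afterwards, for subjects in the primary population.

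The size is 0 to 8 subjects per arm of 40, at most 20% of an arm. It rests on two assumptions: that the planned allowance is an upper limit, and that some sites act on 8.4 without footnote b. No bias in the treatment difference can be derived from the documents.

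**What to change.** Amend Section 8.4 in two respects:

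1. **Cross-reference.** Cite 10.2.2.7 for subjects who stop drug in the Double-blind Period, and keep 10.2.4.6 for those who stop in the OLE.
2. **Follow-up.** Reconcile 8.4 with footnote b and 11.2.4 by stating that stopping study drug does not by itself end data collection. Subjects who stop drug but remain willing and able to attend keep their scheduled double-blind assessments, including Day 90.

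The wording must leave intact 8.4's own reasons that rule out further participation (undue burden, or an exclusion criterion that precludes it) and the ET assessments that Section 11.3.2 requires on pregnancy. It concerns data collection only and does not alter who stops treatment, when or why.

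The cost is a wording amendment. The visits are already in Table 2-1; the downside is some extra visits for subjects no longer on drug. The documents give no budget, so the expense of those visits cannot be stated.

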8.5. Subject Replacement Criteria

Withdrawn subjects will not be replaced. If a substantial number of subjects are withdrawn from the study, the sponsor will evaluate the need for developing replacement criteria.

Randomized subjects withdrawn from the study may not reenter. The subject number for a withdrawn subject will not be reassigned to another subject.

9. TREATMENTS

9.1. Identification of Investigational Product(s)

Trifarotene cream HE1 is a cream containing 100 or 200 µg/g (0.01% [w/w] or 0.02% [w/w], respectively) of CD5789 and the following excipients: purified water, propylene glycol, allantoin, glycerin, medium-chain triglycerides, polypropylene glycol 15 stearyl ether, cyclomethicone, phenoxyethanol, copolymer of acrylamide and sodium acryloyldimethyltaurate, dispersion 40% in isohexadecane (simulgel 600 PHA), sodium benzoate, butylated hydroxytoluene, and gluconolactone. It is an RAR γ agonist characterized by its high specificity to this receptor.

Sodium benzoate, butylhydroxytoluene, and propylene glycol are excipients known to have a recognized action or effect to be declared on the labeling, according to the Committee for Medicinal Products for Human Use Annex to the excipients in labeling and package leaflet of medicinal products for human use (EMA/CHMP/302620/2017). These 3 excipients are being used in the trifarotene formulation at standard concentrations and are all necessary to ensure adequate protection of the formulation along and the shelf life.

Vehicle contains the same ingredients, without the CD5789.

Trifarotene cream HE1 and vehicle will be provided in cream form for topical application and will be supplied in 50-g tubes from which a maximum of 36 g of IP may be extracted.

Trifarotene cream HE1 and vehicle will be supplied by G. Production, Inc. (Galderma) in Baie-D'Urfé, QC, Canada.

9.2. Treatments Administered

For the Double-blind Treatment Period, trifarotene cream HE1 100 µg/g or 200 µg/g or vehicle cream will be applied topically twice weekly on up to 90% BSA of each subject. The IP should be applied thinly and gently rubbed in.

Study staff will apply the first administration of IP in the clinic on Day 1 after Baseline measurements, and the amount of IP used will be measured (i.e., 50-g tube will be measured before and after application to determine amount used). If the product will be applied at home by someone other than the study subject, it is recommended that this person assist with application at the first visit to learn how the IP is applied.

The maximum dose per application is 36 g (i.e., 1 tube). Subjects will receive an adequate number of tubes to use 1 tube per application and will use a new tube for each treatment day. Subjects may use less than full amount of product in a tube. Subjects will apply treatment for 90 days.

After the Day 1 visit, subjects will apply up to 36 g of study drug as for the first dose on up to 90% of BSA twice weekly, sparing the scalp, inguinal, and axillary areas. Subjects with heavy facial hair should not apply IP to hair-bearing areas. Persons other than the study subject applying the study drug must wash their hands after application or use disposable vinyl gloves. In addition, a long-handled applicator will be provided for application on the back. The applicator must be washed with warm water and soap after every application.

Trifarotene cream should not come into contact with the eyes, mouth, angles of the nose, or mucous membranes. For the ectropion treatment, Q-tips are recommended for precise application on eyelids, without contact to the eye or conjunctiva. If the IP gets into the eye, it must be flushed

immediately with warm water. In case of eye irritation, the subject must be seen by an ophthalmologist.

For the OLE, all subjects will receive open-label trifarotene cream HE1 200 µg/g and apply it in the same manner as in the Double-blind Period for an additional 90 days.

Visits for PK must occur at least 24 hours after the last application of the IP to avoid contamination of the blood samples with any IP that may have remained in the skin after the last application. Subjects should not apply IP on visit days until after the visit, unless they are participating in the PK substudy, in which case the IP will be applied in the clinic on Day 1 and Day 30 after the blood draw. Among subjects participating in the PK substudy, ensure the PK line is inserted before study drug application to prevent contamination with the IP and to protect the skin around the needle insertion point from study drug application.

